11.2.3 Source document requirements and document access during the study

The Investigator must retain a comprehensive and centralized filing system of all study-related documentation (including, but not limited to: essential documents, copies of protocols, eCRFs, source data such as original reports of test results, study medication dispensing logs, correspondence, records of informed consent, and other documents pertaining to the conduct of the study) that is suitable for inspection by the Sponsor and representatives of regulatory authorities.

The Investigator/institution will permit study-related monitoring, audits, IRB reviews, and regulatory inspections providing direct access to source data/documents.

11.2.4 Study records retention

Study-related documentation must be kept for at least 25 years or until notified by the Sponsor. Documents should be stored in such a way that they can be accessed/data retrieved at a later date. Consideration should be given to security and environmental risks.

No study document will be destroyed without prior signed agreement between the Sponsor and the Investigator. Should the Investigator wish to assign the study records to another party or move them to another location, written agreement must be obtained from the Sponsor.

11.2.5 Protocol deviations

The Sponsor does not allow prospective deviations from the protocol. Any significant deviations affecting subject eligibility and/or safety must be reviewed or approved by the IEC/IRB and regulatory authority, as applicable. The Investigator is responsible for complying with all protocol requirements, and applicable to laws pertaining to protocol deviations. If a protocol deviation occurs (or is retrospectively identified) after a subject has been enrolled, the Investigator is responsible for notifying their IEC/IRB, regulatory authorities (as applicable), and assigned Clinical Monitor or Sponsor.

11.3 Central reading of transvaginal ultrasound

The scans will be performed locally by qualified personnel and blinded review will be conducted centrally.

11.4 Endometrial biopsy adjudication committee

An endometrial biopsy adjudication committee, composed of three pathologists, will be established for MT-8554-A02. The endometrial tissue obtained by endometrial biopsy will be processed in the same manner by a central laboratory. Three independent expert pathologists, blinded to treatment group and to each other's readings, determine the diagnosis for endometrial biopsy slides during the conduct of the study.

A charter for adjudication committee will outline the scope and key responsibilities, timing of reviews, communications between the adjudication committee, the Investigator site and the Sponsor.

11.5 Study monitoring

In accordance with applicable regulations, GCP, and the procedures of the Sponsor or its designees, the Study Monitor will periodically contact the Investigator site, and conduct on-site visits. The extent, nature, and frequency of on-site visits will be based on study complexity, enrolment rate, and data quality at the Investigator site. Through these visits and frequent communications (e.g., letter, email, and telephone), the Study Monitor will verify that the investigation is conducted according to protocol, regulatory and Sponsor requirements.

The Investigator will allow the Study Monitor direct access to all relevant documents, and allocate his/her time and the time of his/her personnel to the Study Monitor to discuss findings and any relevant issues.

In addition to contacts during the study, the Study Monitor will contact the Investigator site personnel prior to the start of the study to discuss the protocol and data collection procedures.

At study closure, the Study Monitor will conduct all activities as indicated in Section 11.7.

11.6 Quality assurance and auditing

Authorized representatives of the Sponsor, IRBs, and/or regulatory authorities may conduct an audits or inspections of this study either during or after completion. In such cases, the Investigator will give the auditor/inspector direct access to all relevant documents and source data, and will allocate his/her time and the time of his/her personnel as may be required to discuss findings and any relevant issues.

11.7 End of study and site closure

The end of the study is defined as the last visit for the last subject. Upon completion of the study, or if the study or an Investigator site is prematurely discontinued, the following activities, where applicable, must be conducted by the Study Monitor in conjunction with the Investigator:

- Return of all study data to the Sponsor

- Completion of data clarifications and/or resolutions
- Accounting, reconciliation, and final disposition of used and unused study medication
- Review of Investigator site study records for completeness

Any unresolved AEs or SAEs will be followed according to Section 8.10.

11.8 Premature discontinuation of the study

The Sponsor reserves the right to discontinue the study because of safety concerns, ethical issues or serious and/or persistent non-compliance with the protocol.

If the study is suspended or terminated, the Sponsor will promptly inform the Investigator, and will also inform the regulatory authorities of the suspension or termination of the study and the reason(s) for the action. The Investigator is responsible for promptly informing the IRB, and providing the reason(s) for the suspension or termination of the study.

For all subjects, the Follow-up visit assessments should be performed, as far as possible (Section 5.2.2).

Any unresolved AEs or SAEs will be followed up according to Section 8.10.

In the event that a subject elects not to return to the clinic for the EOS visit, the Investigator must make every effort to contact the subject to review all AEs. In the event that a subject drops out of the study at any time, the reason for discontinuation must be fully documented in the source documents and the eCRF. The Investigator site personnel will document the AEs and any other assessments in the source documents and will make every effort to complete all required EOS assessments.

In addition, all general Investigator site activities required for the scheduled EOS and site closure should be completed, as described in Section 11.7.

11.9 Premature discontinuation of individual Investigator sites

The Sponsor may at any time, at its sole discretion, discontinue the Investigator site for various reasons, including, without limitation, the following:

- Failure of the Investigator to comply with applicable laws and/or pertinent regulations
- Submission of knowingly false information from the research facility to the Sponsor, Study Monitor, or regulatory authorities
- Insufficient adherence to protocol requirements

The Sponsor will issue a written notice to the Investigator, which will contain the reasons for taking such action. If the Investigator site is terminated for non-compliance, appropriate regulatory authorities will also be notified by the Sponsor.

For all subjects, the Follow-up visit assessments should be performed, as far as possible (Section 5.2.2).

Any unresolved AEs or SAEs will be followed up according to Section 8.10.

In the event that a subject elects not to return to the clinic for the EOS visit, the Investigator must make every effort to contact the subject to review all AEs. In the event that a subject drops out of the study at any time, the reason for discontinuation must be fully documented in the source documents and the CRF. The Investigator site personnel will document the AEs and any other assessments in the source documents and will make every effort to complete all required EOS assessments.

In addition, all general Investigator site activities required for the scheduled EOS and site closure should be completed, as described in Section 11.7.

11.10 Liability and insurance

Please refer to the written study information given to the subject.

12 DISCLOSURE OF DATA

12.1 Confidentiality

All information concerning MT-8554 is the sole property of the Sponsor. For the avoidance of doubt, the Sponsor has full ownership of the eCRFs completed as part of the study. The Investigator will agree to use the information only for the purposes of carrying out this study and for no other purpose unless prior written permission from the Sponsor is obtained.

Subjects will be informed that all personal information made available for inspection will be handled in the strictest confidence and in accordance with applicable laws and regulations. All personnel involved in the study will observe and work within the confines of applicable data protection regulations.

12.2 Publication

By signing the study protocol, the Investigator agrees that the results of the study may be used for the purposes of national and international registration, publication, and information for medical and pharmaceutical professionals by the Sponsor. If necessary, the regulatory authorities will be notified of the Investigator's name, address, qualifications, and extent of involvement.

The Sponsor will retain ownership of all data. All proposed publications based on the study will be subject to the Sponsor's approval requirements.

The Sponsor or designee will prepare a final report on the study. The Investigator's right to publish or present any information on the study, and publication procedures to be followed, will be defined in the Investigator site agreement.

**LIST OF ABBREVIATIONS**

Abbreviation	Definition
AE	Adverse event
ALP	Alkaline phosphatase
ALT	Alanine aminotransferase
AST	Aspartate aminotransferase
BDRM	Blind data review meeting
BLQ	Below the limit of quantification
BMI	Body mass index
BUN	Blood urea nitrogen
CI	Confidence interval
CPK	Creatine phosphokinase
CRF	Case Report Form
CRO	Contract Research Organization
CS	Clinically significant
CSR	Clinical study report
DMC	Data Monitoring Committee
DP	Decimal places
E2	Estradiol
ECG	Electrocardiogram
eCRF	Electronic Data Collection Form
EOS	End of study
EOT	End of treatment
FDA	Food and Drug Administration
Fmi	Daily frequency of mild VMS
Fmo	Daily frequency of moderate VMS
Fse	Daily frequency of severe VMS
FSH	Follicle stimulating hormone
GAD7	7-Item Generalized Anxiety Disorder questionnaire
GCP	Good Clinical Practice
IAO	International Agreed Order
ICF	Informed Consent Form
ICH	International Conference on Harmonization

Abbreviation	Definition
IEC	Independent Ethics Committee
IRB	Institutional Review Board
IMP	Investigational medicinal product
IND	Investigational New Drug Application
ITT	Intent-to-Treat
IVRS	Interactive Voice Response System
IWRS	Interactive Web-based Response System
LDH	Lactate dehydrogenase
LDL-C	Low density lipoprotein-cholesterol
LH	Luteinizing hormone
LLOQ	Lower limit of quantification
MCH	Mean corpuscular hemoglobin
MCHC	Mean corpuscular hemoglobin concentration
MCV	Mean corpuscular volume
MedDRA	Medical Dictionary for Regulatory Activities
MENQOL	Menopause-Specific Quality of Life questionnaire
MsFLASH	Menopausal Strategies: Finding Lasting Answers to Symptoms and Health
MTDA	Mitsubishi Tanabe Pharma Development America, Inc.
MTPC	Mitsubishi Tanabe Pharma Corporation, Inc.
NCS	Not clinically significant
PHQ-8	8-Item Patient Health Questionnaire
PT	Preferred term
QC	Quality control
QOL	Quality of life
QTc	Corrected QT interval
QTcF	Corrected QT interval using Fridericia's formula
RBC	Red blood cells
SAE	Serious adverse event
SAF	safety population
SAP	Statistical Analysis Plan
SD	Standard deviation

Abbreviation	Definition
SNRI	Serotonin-norepinephrine reuptake inhibitors
SOC	System Organ Class
SSRI	Serotonin reuptake inhibitors
SUSAR	Suspected unexpected serious adverse event
TEAE	Treatment-emergent adverse event
THC	Tetrahydrocannabinol
ULN	Upper limit of normal
US	United States
VMS	Vasomotor symptoms
WBC	White blood cells
WHO	World Health Organization
WMA	World Medical Association

## 1. INTRODUCTION

This statistical analysis plan (SAP) is based on the MT-8554-A02 final protocol and amendment 4 dated 07 August 2019. The plan covers statistical analysis, tabulations and listings of efficacy, safety data to assess the efficacy and safety of MT-8554(10 mg initially, switched to 5 mg).

The SAP is prepared by MTD data science and reviewed by MTD clinical study team and MTPC data science. The statistical analyses and production of the outputs described in the SAP will be conducted and QCed by [REDACTED] using SAS version 9.4 or higher. The final analyses and outputs will be approved by MTPC/MTD data science.

## 2. STUDY OBJECTIVE AND ENDPOINTS

### 2.1 Study Objectives

#### Primary Objective:

- To assess long-term safety and tolerability of MT-8554.

#### Secondary Objectives:

- To assess long-term efficacy of MT-8554 on VMS frequency and severity.
- To assess long-term efficacy of MT-8554 on quality of life as measured by Menopause Specific Quality of Life (MENQOL).

### 2.2 Study Endpoints

#### 2.2.1 Safety Endpoints (Primary Endpoints)

- Physical examination (including breast safety evaluation).
- Vital signs (blood pressure, pulse and tympanic body temperature).
- Electrocardiogram (ECG) parameters (including cardiac intervals: heart rate, PR, QRS, QT, QTcF and QTcB).
- Clinical laboratory assessments (hematology, biochemistry, coagulation and urinalysis).
- Reproductive hormones (luteinizing hormone [LH], follicle stimulating hormone [FSH], and estradiol [E2]).
- Adverse events (AEs).
- Endometrial safety (endometrial thickness as measured by transvaginal ultrasound, and incidence of endometrial hyperplasia as measured by endometrial biopsy).
- Breast safety (breast tenderness and incidence of breast cancer).
- Depression and anxiety as measured by 8-Item Patient Health Questionnaire (PHQ-8) and by Generalized Anxiety Disorder-7 (GAD7), respectively.

## **2.2.2 Exploratory Endpoints**

- Frequency of VMS, which is the average daily frequency of moderate to severe VMS, defined as the sum of the number of moderate to severe VMS during 1 week divided by number of days with data.
- Severity of VMS, which is the average daily severity score of mild to severe VMS. Baseline VMS severity score and VMS severity score for a specific week during the open label treatment period is defined as  $(1xFmi + 2xFmo + 3xFse)/(Fmi + Fmo + Fse)$ , where Fmi, Fmo, and Fse are the daily frequencies of mild, moderate, and severe VMS, respectively, during each applicable study week.
- MENQOL.

## **3. STUDY DESIGN**

### **3.1 Study Design**

[figure not shown]
Study MT-8554-A02 is an open-label, long-term safety extension trial of Study MT-8554-A01. The study will be initiated during the conduct of Study MT-8554-A01.

Subjects who complete the preceding trial (Study MT-8554-A01) and comply with eligibility criteria for Study MT-8554-A02 will be enrolled in a 52-week open-label treatment period. Visit 7 (Week 12) of Study MT-8554-A01 will be considered Visit 1 of Study MT-8554-A02. Assessments already carried out at Visit 7 (Week 12) of Study MT-8554-A01 will not be repeated. During the 52-week open-label treatment period, subjects will attend visits every 8 weeks between Visits 1 and 3 (Weeks 12, 20, and 28) and every 12 weeks between Visits 3 and 6 (Weeks 28, 40, 52, and 64).

All enrolled subjects will receive MT-8554 (10 mg initially, switched to 5 mg\*) for 52 weeks. Study drug will be administered once daily before bedtime.

An End of Study (EOS) Follow-up visit will be conducted by phone for safety follow-up 30 days after the end of the open-label treatment period.

\*Note: Based upon the results of Study MT-8554-A01, the dose is changed from 10 mg to 5 mg because participating subjects will no longer derive potential clinical benefit from receiving 10 mg dose. All participating subjects who reconsent to continue the study will receive MT-8554 5 mg.

**Figure 1 Study Design Schematic**

### 3.2 Schedule of Study Procedures

Study assessments are summarized in the Time and events schedule (Table 1).

**Table 1 Schedule of Assessments**

Study Period	Open-label extension						Follow-up
	Visit 1 	Visit 2	Visit 3	Visit 4	Visit 5	Visit 6 (EOT)	
Visit Number							Visit 7 (EOS)
Study Week 	Week 12 	Week 20	Week 28	Week 40	Week 52	Week 64 	Week 68 
Study Day ±Window 	Day 85 ±3	Day 141 ±7	Day 197 ±7	Day 281 ±7	Day 365 ±7	Day 448 ±7	Day 476 ±7
Informed consent	X						
Inclusion/exclusion criteria	X						
Physical examination 	X	X	X	X	X	X	
Breast examination	X						X
Body weight	X			X			X
Vital signs 	X	X	X	X	X	X	
12-lead ECG	X			X			X
Routine lab tests	X	X	X	X	X	X	
Transvaginal ultrasound 	X						X
Endometrial biopsy 	X						X
Reproductive hormones 	X						X
PHQ-8 and GAD7	X		X				X
VMS diary	<—————>						
MENQOL	X		X				X
Dispensing MT-8554 	X	X	X	X	X		
Drug accountability	X	X	X	X	X	X	
Adverse events	<—————>						
Concomitant medication	<—————>						
Compliance █ Calls to Subjects 	<—————>						

Abbreviations: ECG=Electrocardiogram; EOS=End of Study; EOT=End of Treatment Visit; GAD7=Generalized Anxiety Disorder-7 Questionnaire; MENQOL=Menopause Specific Quality of Life; PHQ-8=Eight-Item Patient Health Questionnaire; VMS=vasomotor symptoms.

1. Visit 7 (Week 12) of Study MT-8554-A01 will be considered Visit 1 of Study MT-8554-A02.
2. Study weeks and study days are in reference to the randomization performed on Day 1 in Study MT-8554-A01.
3. Assessments already carried out at Week 12 of Study MT-8554-A01 will not be repeated.
4. The EOT should be performed for subjects who complete treatment as well as those who withdraw from the study early.
5. The Follow-up visit, EOS, will be conducted by phone 30 days after the EOT visit for subjects who complete as well as those who withdraw early from the study.
6. Physical examination (abdominal, cardiovascular, general appearance, respiratory, and other) will be performed.
7. Vital signs (including sitting blood pressure, pulse rate, and tympanic body temperature) will be measured at all visits.
8. Transvaginal ultrasound and endometrial biopsy to be performed only on subjects who have a uterus. Pelvic examination will be performed only with endometrial biopsy.
9. Luteinizing hormone (LH), follicle stimulating hormone (FSH) and estradiol (E2) will be measured.

10. Subjects will receive 5 mg\* of MT-8554 once daily. Investigators should instruct subjects to administer dose at least 2 hours after starting the evening meal and approximately 30 minutes before bedtime.  
\*Note: Based upon the results of Study MT-8554-A01, the dose is changed from 10 mg to 5 mg because participating subjects will no longer derive potential clinical benefit from receiving 10 mg dose. All participating subjects who reconsent to continue the study will receive MT-8554 5 mg.

11. Site staff will make periodic calls to the subjects at a minimum of every 4 weeks where no in-clinic visits occur, to confirm compliance with daily VMS diary data entry [REDACTED] requirements.

### **3.3 Sample Size and Power Considerations**

This study is an open-label extension of Study MT-8554-A01. There is no formal sample size estimation for this study. It is planned to enrol up to 364 subjects from Study MT-8554-A01. The subjects who have completed Study MT-8554-A01 and comply with all eligibility criteria may be enrolled into this study.

## **4. PLANNED ANALYSES**

This SAP will be finalized before database lock. Final data analysis will be conducted after database lock.

There is no plan for analyses other than final data analysis .

## **5. ANALYSIS POPULATION(S)**

Statistical analyses will be based on separate population sets, defined in Table 2.

**Table 2 Analysis populations**

Analysis Population	Definition
Safety(SAF) population	All subjects who receives at least 1 dose of study medication
Intent-to-treat (ITT) population	All subjects who have at least 1 post-baseline exploratory assessment

## **6. GENERAL CONSIDERATIONS**

### **6.1 Descriptive Statistics**

Continuous data will be summarized descriptively using the number of observations, mean, standard deviation (SD), median, minimum and maximum. Categorical data will be summarized using frequency counts and percentages. The denominator for the percentages will be the total number of subjects in the treatment group and analysis population being presented, unless otherwise specified.

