## **7. DATA CONVENTION**

### **7.1 Data Handling Convention for Dropouts or Missing Data**

For each summaries, only observed data will be used. Unless otherwise specified missing data will not be imputed. Unless otherwise specified, summary statistics will be calculated as long as one non-missing value exists.

For AE start and/or end date missing or partial missing, the AE will be treated as TEAE if it cannot be determined a non-TEAE. If severity or relationship is found to be missing the most severe occurrence will be imputed for the particular summary.

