#### **8.2.7.1 Endometrial Thickness Measured by Transvaginal Ultrasound (TVU)**

The endometrial thickness as measured by TVU will be summarized in the tables by treatment group of A01 and overall and visit as below. (Table 14.3.6.1, Table 14.3.6.2)

1. Summary table presenting mean and SD for baseline, post baseline visits and change from baseline
2. Summary table of endometrial thickness by category (<5 mm, 5 to 8 mm, >8 mm)
3. Summary table for category of change from baseline (>3 mm, >5 mm)

The central reading data will be used for the analysis.

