### 8.2.7.2 Endometrial Histology (Endometrial Biopsy)

The Endometrial biopsy data will be summarized in the tables by treatment group of A01 and overall and visit as below.

1. Summary tables of proportion of subjects in abnormal\* category (Table 14.3.7.1)
2. Shift table for change in abnormal category from baseline to week 64 or EOT(Table 14.3.7.2)

\*Note: The histological categories are based on 2003 draft FDA guidance. [REDACTED]

[REDACTED]

[REDACTED]

[REDACTED]

The data from adjudication committee will be used for the analysis.

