### 8.4 Dose Change

All subjects were treated with MT-8554 10 mg initially. Then from protocol amendment 4, all subjects remaining in study changed to MT-8554 5 mg. Some subjects already completed or discontinued the study. To compare the data before and after the dose change, the following analyses will be conducted.

No.	Title of Table	Analysis Population
14.1.5	Summary of Exposure to Study Medication: Duration of exposure the dose change	SAF
14.3.1.1	Summary of Treatment Emergent Adverse Events (TEAE)	SAF
14.3.1.1.Ex4Site	Summary of Treatment Emergent Adverse Events (TEAE -Exclude 4 Florida site-	SAF

No.	Title of Table	Analysis Population
14.3.1.2	Incidence of Treatment Emergent Adverse Events by System Organ Class, Preferred Term	SAF
14.3.1.2.Ex4Site	Incidence of Treatment Emergent Adverse Events by System Organ Class, Preferred Term -Exclude 4 Florida site-	SAF
14.3.1.4	Incidence of Treatment Emergent Adverse Events by System Organ Class, Preferred Term and Severity for before the dose change	SAF
14.3.6.1	Transvaginal Ultrasound (TVU)	SAF
14.3.6.1. Ex4Site	Transvaginal Ultrasound (TVU) -Exclude 4 Florida site-	SAF
14.3.6.2	Transvaginal Ultrasound (TVU) - Endometrial Thickness	SAF
14.3.6.2. Ex4Site	Transvaginal Ultrasound (TVU) - Endometrial Thickness -Exclude 4 Florida site-	SAF

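### The SAP's default percentage denominator, all dosed subjects, is not overridden for the endometrial thickness categories, although only women with a uterus are scanned

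*SAP*

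**What the plan says.** - **Default denominator.** SAP 6.1: "The denominator for the percentages will be the total number of subjects in the treatment group and analysis population being presented, unless otherwise specified".
- **Population.** SAP Table 2 defines the safety population as "All subjects who receives at least 1 dose of study medication". It sets no condition on having a uterus or on being examined. The lists in SAP 8.4 and 8.5 assign this population to Tables 14.3.6.1 and 14.3.6.2 (the latter titled "Transvaginal Ultrasound (TVU) - Endometrial Thickness"). SAP 8.5 also assigns it to the site-excluded biopsy table, 14.3.7.1.Ex4Site.
- **Who is examined.** Footnote 8 of the assessment schedule (Table 1 in both documents) and protocol 6.5.5 and 6.5.6 limit ultrasound and biopsy to women with a uterus. The synopsis admits surgically menopausal women, and no inclusion criterion in protocol 4.3 requires a uterus.
- **Thickness tables.** SAP 8.2.7.1 asks for mean and SD, for three thickness categories (below 5, 5 to 8, above 8 mm), and for a "Summary table for category of change from baseline (>3 mm, >5 mm"), each by A01 treatment group, overall and visit. It says that central readings are used. It gives no denominator, and no redaction is visible in it.
- **Biopsy tables.** SAP 8.2.7.2 asks for "Summary tables of proportion of subjects in abnormal" category and for a "Shift table for change in abnormal category from baseline to week 64 or EOT". The note on the categories is followed by redacted lines.
- **Missing data.** SAP 7.1: "For each summaries, only observed data will be used".

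**The concern.** Endometrial thickness and the incidence of hyperplasia are named safety endpoints under the primary objective (protocol 2.2.1, SAP 2.2.1). A woman who cannot be scanned, or was not scanned, is not at risk of being recorded in any thickness category. Counting her in the denominator treats her as examined and free of the finding.

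Three things follow if the default is programmed as written. The percentage above 8 mm, or with an increase above 3 or 5 mm, is lower than the proportion among women examined. The three thickness categories, which cover every possible reading, do not add to 100%. And because the default is applied within each A01 treatment group, groups with different shares of unscanned women are diluted to different degrees, which blurs the comparison between columns. If no case occurs, the percentage is 0% either way, but what a zero rules out depends on the number examined, not on the number dosed.

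**Working it through.** The plan gives no rate, power or sample-size figure on this point, so there is nothing to reproduce. The check traces the rule and then sizes it under stated assumptions.

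**Step 1: trace the rule.** SAP 6.1 applies unless another denominator is specified. The visible text of SAP 8.2.7, 8.4 and 8.5 specifies none for thickness. The population attached to the tables is the safety population. The literal denominator is therefore everyone dosed, within each A01 group and overall.

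**Step 2: formula.** Let N be the number dosed, h the share without a uterus, c the share of women with a uterus who have an evaluable scan, and x the number with a finding.
- Number examined: n = N × (1 − h) × c
- Planned percentage: x/N. Percentage among women examined: x/n
- Ratio of the two: N/n
- Sum of the three thickness categories as planned: n/N
- Zero findings, exact two-sided 95% upper limit: 1 − 0.025^(1/n)

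**Step 3: inputs.** N = 364 is the enrolment ceiling in protocol 4.1, used for illustration. Neither h nor c is in the documents; both are assumptions.

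**Step 4: results with every eligible woman scanned (c = 1).**

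| h (assumed) | n | N/n | Categories sum to | One finding: planned | One finding: among examined | Zero findings: upper limit on n |
|---|---|---|---|---|---|---|
| 0% | 364 | 1.00 | 100% | 0.27% | 0.27% | 1.01% |
| 20% | 291 | 1.25 | 80% | 0.27% | 0.34% | 1.26% |
| 30% | 255 | 1.43 | 70% | 0.27% | 0.39% | 1.44% |

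**Step 5: missing scans add to this.** Protocol 4.5.2 asks for end-of-treatment assessments after withdrawal only as far as possible, so c may be below 1. For illustration, take h = 20% and c = 60%. Then n = 364 × 0.8 × 0.6 = 175, the categories sum to 175/364 = 48.1%, and N/n = 2.08. Ten findings would read 10/364 = 2.75% instead of 10/175 = 5.71%. Missing scans dilute the percentage even if h = 0.

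**Step 6: where early-termination scans go (secondary).** SAP Table 3 has no window for Days 86 to 112, which is 112 − 86 + 1 = 27 days. Early-termination scans on Days 113 to 407 fall in the Week 20 to Week 52 rows, where no scan is scheduled. When a window holds several visits, SAP 7.2 keeps the visit closest to the nominal day. If that rule is applied to visits, a routine visit without a scan can displace a later early-termination visit with one. With routine visits on the nominal day, the affected days are 142–169, 198–239, 282–323 and 366–407, or 28 + 42 + 42 + 42 = 154. With routine visits 7 days early or late, each window loses 7 of these, giving 154 − 28 = 126. Adding the 27 days gives 153 to 181 of the 322 days from Day 86 to Day 407. If the rule is applied to each result, only the 27 days are affected. These are calendar days, not women.

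**The case against.** The best counter-argument is SAP 7.1. It covers every summary, and a percentage of observed scans is a natural reading of it; an experienced programmer might well do that. This stands in part: it shows that the plan can be read two ways. It does not remove the problem, because 7.1 concerns missing values and names no denominator, whereas 6.1 names one expressly and says when it may be replaced.

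Second, the number examined is largely available already. SAP 6.1 and 9.1 require the number of observations for continuous summaries, so Table 14.3.6.1 should show the number scanned in each row, and all endometrial data are listed. This stands. A reader might infer that the plan hides how many women were scanned; it does not. The fault is in the percentages of the category tables.

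Third, a reader might infer that hyperplasia incidence is certainly understated too. The documents do not support that. The redacted lines in SAP 8.2.7.2 may set a biopsy denominator, and redacted text cannot be counted as absent. The thickness section shows no redaction, though the SAP contents page has blacked-out entries after Section 11 whose content is unknown.

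Fourth, the size is assumed, and its range begins at no effect. This stands. It would also be wrong to read 364 less about 100 completers as a planned 264 non-completers: 364 is a ceiling, and protocol 4.6 requires end-of-treatment assessments of all subjects when the study is completed.

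Finally, a reader might infer from the window rules that early-termination findings disappear. They do not. Early-termination biopsies enter the shift table, all endometrial data are listed, and findings judged clinically significant are recorded as adverse events (protocol 8.8).

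**Conclusion.** The point holds for the ultrasound category tables. As written, the SAP's explicit default gives percentages of thickness category and of change category over everyone dosed, although only women with a uterus are scanned. SAP 7.1 suggests otherwise without saying so, and the two sections must be reconciled. For the biopsy-abnormal proportion the point is conditional on what the redacted lines say.

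The true size is unknown. With an assumed 0 to 30% without a uterus and complete scanning, the proportion among women examined is 1.00 to 1.43 times the printed one, and the ratio is larger if scans are missing. Counts, mean and SD of thickness, and the number of observations are not affected. The analysis is descriptive, so no test or decision threshold changes. It should be fixed because it concerns a safety endpoint under the primary objective and the correction costs almost nothing. The handling of early-termination scans is a smaller, separate matter that depends on how the window rule is programmed.

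**What to change.** In SAP 8.2.7:
1. State that percentages in the endometrial tables use, as denominator, women in the safety population who have a uterus and an evaluable result at that time point: a central reading for ultrasound, an adjudicated result for biopsy. For change-category and shift tables, require both a baseline and a post-baseline result. Say that this replaces the default in 6.1. If the redacted biopsy text already sets a denominator, check that it agrees.
2. Print that N in each column and row.

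Secondary:

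3. Add a row for Week 64 or early termination (last post-baseline result) to the thickness tables, matching the biopsy shift table.
4. State that the visit windows are applied per result for these procedures, so that a visit without a scan cannot displace one with a scan.

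The cost is a few SAP sentences and some table rows, with no new procedures or data. Percentages become slightly less favourable if a case occurs.
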